1. SYNOPSIS

Methodology:

This single center, 15-day clinical trial is being conducted to assess the changes to the skin microbiome of induced wounds on the back in approximately 35 healthy adult subjects aged 18-55 years, with Fitzpatrick Skin Types I – III. There will be 6 test sites randomly assigned to treatments for each subject. Four of the test sites will be wounded and covered with various marketed adhesive bandages, one test site will be wounded and un-covered (positive control) and one test site will remain intact and un-covered (negative control). Following a screening visit (3-14 days prior to Visit 2) and a 3-day washout period, subjects will be assessed at Baseline (Day 0), Days 1 – 7 and Day 14; subjects will also return to the study site daily for bandage changes.

The following assessments will be performed by trained study staff at Baseline (Day 0), Days 1-7, and Day 14:

- **Microbiome** [REDACTED]: Swabs will be used to collect bacteria [REDACTED] from the test site surfaces. A total of 2 swabs will be taken per test site per timepoint.
- **Trans Epidermal Water Loss (TEWL; tewameter):** Noninvasively measures water evaporation from the skin, which is a measure of skin barrier function. These measurements will be done three times for each test site.
- [REDACTED]
- **Skin pH (Skin pH Meter PH905):** Noninvasively measures skin surface pH. [REDACTED]
- **Diffuse Reflectance Spectroscopy (DRS):** Noninvasively measures redness by oxy-, deoxy-hemoglobin, and melanin levels in the skin. Five repetitive spectra acquisition will be implemented for each test site.
- [REDACTED]

A randomization code will designate which wound will receive the appropriate treatment. Study bandages will be changed daily (by study staff on each day of the

study Days 1 -14). Subjects will report back to the study facility for daily bandage changes (Days 1-14) and for assessments on Days 1-7 and 14.

Adverse events will be monitored throughout the study.

Number of subjects (planned):

A sufficient number of subjects will be screened, approximately 35 subjects will be randomized to ensure completion of at least 30 subjects

Diagnosis and main criteria for inclusion:

Adults aged 18-55 who meet the inclusion criteria and none of the exclusion criteria, which include generally healthy male or female subjects with Fitzpatrick skin types I-III and who agree to the requirements of the study, will be eligible for the study.

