14. STATISTICS

The Sponsor will be responsible for the data management and statistical analyses of this study. The skin microbiome [REDACTED] data will be analyzed and reported independently by external partners. The imaging data will be analyzed by the sponsor.
Sample Size Determination

The sample size of this exploratory study is not based on the statistical power consideration.

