14.2. Efficacy Analysis

The analysis of the predominant microflora will be performed by Research and Testing Laboratories, LLC (external partner).

TEWL, [REDACTED] and DRS are measured at Baseline, Days 1-7 and Day 14. The triplicate values at each assessment time point will be averaged as the final response value, with the exception of the DRS which will have 5 replicates at each timepoint.

The final response values of TEWL and DRS will be summarized at each assessment time point by the assigned test products.

The within product comparison will be performed using the paired t-test to compare the values of each product at each post baseline time point with its own baseline value.

The between products comparison will be performed based on the change from baseline (post baseline value minus baseline value). The change from baseline of each product will be analyzed using mixed effect ANCOVA model at each post baseline time point. The ANCOVA model will include the product as the factor and the baseline value as the covariate. The model will include the subject as a random effect to incorporate the within subject correlation. The adjusted mean of each product from the ANCOVA model will be compared between the test products and the negative control, between the test products and the positive control, and between the negative control and the positive control.

[REDACTED]

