1.2 Study Design

This single center, 15-day clinical trial is being conducted to assess the changes to the skin microbiome of induced wounds on the backs of approximately 35 healthy adult subjects aged 18-55 years, with Fitzpatrick Skin Types I – III. There will be 6 test sites randomly assigned to treatments for each subject. Four of the test sites will be wounded and covered with various marketed adhesive bandages, one test site will be wounded and un-covered (positive control) and one test site will remain intact and un-covered (negative control). Following a screening visit (Day -3 to -14) and a 3-day washout period, subjects will be assessed at Baseline (Day 0), Days 1 – 7 and Day 14; subjects will also return to the study site daily for bandage changes.:

The following assessments will be performed by trained study staff at Baseline (Day 0), Days 1-7, and Day 14:

- Microbiome [REDACTED] Swabs will be used to collect bacteria [REDACTED] from the skin surface. A total of 2 swabs will be taken per site per timepoint.
- Trans Epidermal Water Loss (TEWL; tewameter): Noninvasively measures water evaporation from the skin, which is a measure of skin barrier function. These measurements will be done three times for each test site.
- [REDACTED]
- Skin pH (Skin pH Meter PH905): Noninvasively measures skin surface pH. [REDACTED]
- Diffuse Reflectance Spectroscopy (DRS): Noninvasively measures redness by oxy-, deoxy-hemoglobin, and melanin levels in the skin. Five repetitive spectra acquisition will be implemented for each test site.
- [REDACTED].

A randomization code will designate which test site will receive the appropriate treatment. A subgroup of 17 subjects will also be randomly assigned for additional metabolite analysis. Study bandages will be changed daily (by study staff on each day of the study Days 1 -14). Subjects will report back to the study facility for daily bandage changes (Days 1-14) and for assessments on Days 1-7 and 14.

Adverse events will be monitored throughout the study.

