4.5 Covariates

For the analyses of Change from Baseline in TEWL, [REDACTED], skin pH and DRS measurement, corresponding baseline value will be adjusted in the models as covariate.

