6.2 Statistical Decision Rules

The comparison between products will be performed at the 0.05 level of significance, two-sided and all analyses are exploratory. Thus, for any given comparison, the null hypothesis of no difference in treatment means will be rejected if, and only if, the corresponding test p-value is equal to or smaller than 0.05.

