6.3 Statistical Methods

TEWL, ~~SKICON~~, skin pH and DRS are measured at Baseline, Days 1-7 and Day 14. The triplicate values at each assessment time point will be averaged as the final response value, with the exception of the DRS which will have 5 replicates at each timepoint.

The final response values of TEWL, DRS, SKICON and skin pH will be summarized at each assessment time point by the assigned test products.

The within product comparison will be performed using the paired t-test to compare the values of each product at each post baseline time point with its own baseline value.

The between products comparison will be performed based on the change from baseline (post baseline value minus baseline value). The change from baseline of each product will be analyzed using mixed effect ANCOVA model at each post baseline time point. The ANCOVA model will include the product as the factor and the baseline value as the covariate. The model will include the subject as a random effect to incorporate the within subject correlation. The adjusted mean of each product from the ANCOVA model will be compared between the test products and the negative control, between the test products and the positive control, and between the negative control and the positive control.

The mixed effect analysis of covariance model can be performed by the following SAS codes

```
PROC MIXED DATA = <dataset>;
  CLASS subjID treatment;
  MODEL chg = treatment baseline/solution ddfm = contain;
  RANDOM subjID ;
  LSMEANS treatment/diff cl;
  ESTIMATE "Positive Control vs. Negative Control" treatment -1 1 0 0 0 0 /cl;
  ESTIMATE "Product #1 vs. Negative Control" treatment -1 0 1 0 0 0 /cl;
  ...
  RUN;
```

Note:

1. Assume Negative Control = “A”, Positive Control = “B”, Product #1 = “C”, Product #2 = “D”, Product #3 = “E”, Product #4 = “F”.

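### The ANCOVA's single baseline slope mixes within- and between-subject information; adding the subject's mean Day 0 value is an optional, free precision gain, not a validity fix

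*SAP*

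**What the plan says.** The design is a complete block within each subject: "There will be 6 test sites randomly assigned to treatments for each subject" (SAP 1.2). At each post-baseline day, SAP 6.3 regresses change from baseline on treatment and one baseline term, "MODEL chg = treatment baseline/solution ddfm = contain", with a RANDOM statement for subject. SAP 4.5 describes the adjustment as "corresponding baseline value will be adjusted in the models as covariate". Protocol 14.2 describes the same model: "The model will include the subject as a random effect to incorporate the within subject correlation".

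The baseline is site-specific. The paired tests in SAP 6.3 "compare the values of each product at each post baseline time point with its own baseline value", and the change score is built the same way. Neither document splits baseline into a subject mean and a deviation from it, and neither fits subject as a fixed effect.

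The Protocol synopsis plans that "approximately 35 subjects will be randomized to ensure completion of at least 30 subjects". Protocol 14 adds that "The sample size of this exploratory study is not based on the statistical power consideration". No SD, intraclass correlation or baseline-to-follow-up correlation is given.

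**The concern.** Every product versus uncovered-wound contrast is a difference between two sites on the same subject. The adjustment that minimises its variance uses the within-subject slope: how far a site that is above its own subject's mean at Day 0 moves back by Day t. The between-subject slope answers another question, namely whether subjects with a high general level change less.

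The two slopes need not agree. Reading noise and site-to-site deviation can regress quickly while a subject's general level persists, or the reverse. When they differ, the random subject effect is correlated with the baseline covariate, which the planned model assumes away, and the fitted coefficient falls between the two slopes.

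What is at stake is precision only: the width of the four product versus positive-control intervals for each sponsor-analysed endpoint and day.

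**Working it through.** The plan states no precision or power figure, so there is nothing to reproduce. The check asks how far the mixed slope can be from the within-subject slope, and what that costs.

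**Inputs from the documents:** n = 35 subjects (30 completers also tried), k = 6 sites, one baseline slope, random subject intercept. **Assumed:** all variances and correlations.

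**Formulas**
- Contrast estimate = (difference in mean change) − b × (difference in mean Day 0 value).
- Mixed slope: b = (1 − w)·bW + w·bB, with w = (SB/φ) / (SW + SB/φ).
- SW = (n−1)(k−1) × within-subject Day 0 variance. SB = (n−1)k × variance of the subject's Day 0 mean.
- φ = 1 + k × (subject variance left after the slope) / (residual variance). It depends on b, so the equations are solved together.
- Variance ratio, planned model over within-slope model ≈ 1 + (b − bW)² × (within-subject Day 0 variance) / (within-subject residual variance at bW).

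**Bias.** Wounded sites are randomised, so the expected Day 0 difference between two of them is zero. A different b changes the variance of the contrast, not its expectation. In simulation the null rejection rate was 0.046 to 0.053 for both models.

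**Case A, moderate.** Day 0 intraclass correlation 0.7, within-subject correlation 0.2, between-subject correlation 0.8, equal SDs. Slopes are for the Day t value; subtract 1 for change.
- SW = 34 × 5 × 0.3 = 51; SB = 34 × 6 × (0.7 + 0.3/6) = 153.
- bW = 0.20; bB = (0.8 × 0.7 + 0.2 × 0.3/6) / 0.75 = 0.76.
- φ ≈ 9.2, so w = 16.6/67.6 = 0.25 and b = 0.34.
- Ratio = 1 + 0.14² × 0.3/0.288 = 1.02.

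**Case B, extreme.** Within-subject Day 0 variance 1, half of it stable; subject variance 4; subject level fully persistent; no subject-specific change. Slopes are for change.
- SW = 34 × 5 × 1 = 170; SB = 34 × 6 × (4 + 1/6) = 850.
- bW = −0.50; bB = −(0.5/6)/4.167 = −0.02.
- φ ≈ 1.44, so w ≈ 0.78 and b ≈ −0.13 (under-correction).
- Residual variance at bW = 1 − 0.5² = 0.75; ratio ≈ 1 + 0.37²/0.75 = 1.18.

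**Case C, low persistence.** As B, but only 0.2 of the subject level persists, with subject-specific change variance 0.5 × 0.75 = 0.375.
- bB = (−0.8 × 4 − 0.5/6)/4.167 = −0.79; φ ≈ 4.6, so w ≈ 0.52 and b ≈ −0.65 (over-correction).
- Ratio ≈ 1 + 0.15²/0.75 = 1.03.

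**Case D, persistence 0.5.** As B otherwise: bB = (−0.5 × 4 − 0.5/6)/4.167 = −0.50 = bW, so the ratio is 1.00.

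**REML simulation, 6,000 trials per scenario, one wounded site against another**

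| Assumptions | Variance ratio |
|---|---|
| Equal slopes | 0.997–1.000 |
| Within/between correlation 0.3/0.6 | 0.998–1.004 |
| 0.2/0.8 | 1.009–1.033 |
| 0.1/0.9 | 1.016–1.056 |
| 0/0.95, intraclass correlation 0.9 | 1.069 (n = 35), 1.081 (n = 30) |
| Full persistence, 50% stable, subject variance 1×, 2×, 4× | 1.006–1.05, 1.016–1.10, 1.04–1.16 |
| Full persistence, 20% stable, 1× to 4× | 1.01–1.20 |

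In the last two rows subject-specific change variance runs from 1 down to 0 times the residual variance, and the upper ends belong to 0.

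**Degrees of freedom.** Under containment the residual df are 210 − (35 + 5 + 1) = 169 (35 subject columns, 5 further treatment columns, 1 baseline). The subject-mean baseline is constant within subject, so it lies in the span of the subject columns: the rank stays 41 and the df stay 169.

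**The case against.** Baseline-adjusted ANCOVA with a random subject effect is a standard and valid choice, and it already captures most of the gain from adjustment. In the correlation-based scenarios above, unadjusted change scores had 1.2 to 2.0 times the variance of the within-slope model. SAP 6.2 says "The comparison between products will be performed at the 0.05 level of significance, two-sided and all analyses are exploratory". The primary objective is the microbiome, which is analysed externally. An effect with 80% power under the within-slope model keeps about 77% in the worst correlation-based scenario and 79 to 80% in most. The largest losses need every subject to change alike apart from noise, whereas Protocol 11.8.1 itself says that the number of strips needed varies among subjects. All of this stands and limits the weight of the point.

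The added term also has a limit. One slope is still pooled over all six sites. If intact and wounded skin had different baseline slopes, the new coefficient would mix those two, and the subject mean would not cure that.

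What the objection does not remove is the mixing itself, which nothing in either document prevents.

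**Conclusion.** The mixed slope is a real feature of the planned model; its cost is conditional and usually small. Under the assumed variance components, the variance of a product versus uncovered-wound contrast is typically 0 to 7% larger than necessary. At 7% that is 35 × (1 − 1/1.07) = 2.3 subjects' worth of information, or intervals about 3% wider (√1.07 = 1.034). The edge of about 20% (√1.20 = 1.095, or 35 × (1 − 1/1.20) = 5.8 subjects) needs a highly persistent subject level, large subject variance and no subject-specific change.

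A reader might infer more than the documents support:
- *Precision is lost and every such interval is too wide.* With equal slopes the ratio is 1.00, and no stated figure shows that the slopes differ.
- *Baseline differences are under-corrected.* The direction depends on persistence: Case B under-corrects and Case C over-corrects.
- *The analysis is biased or invalid.* Randomisation keeps contrasts between wounded sites unbiased, and test size is nominal.
- *The extra term costs one of the 169 df.* It does not, with complete data.

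Contrasts with the intact site raise a separate question, whether Day 0 is read before or after wounding. This point neither relies on it nor settles it.

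Class: free improvement, optional.

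**What to change.** In SAP 6.3, derive the subject's mean Day 0 value over the test sites (`basemean`) for each measurement and add it beside the site's own baseline: `MODEL chg = treatment baseline basemean / solution ddfm=contain; RANDOM subjID;`. With complete data the baseline coefficient is then the within-subject slope, and all LSMEANS and ESTIMATE contrasts use it. Fitting subject as a fixed effect gives the same slope and contrasts with complete data.

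Make the wording in SAP 4.5, Protocol 14.2 and the Protocol synopsis match. Because SAP 5 excludes imputation, state which sites enter the mean when a site has no value on a given day.

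Cost: one derived variable and one model term. There are no new data, visits or subjects, no loss of within-subject residual df with complete data, and no appreciable loss of precision if the slopes turn out equal.

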6.4 DEMOGRAPHIC AND BASELINE CHARACRISTICS

Summary statistics (number of subjects, mean, standard deviation, median, minimum and maximum) will be provided for numerical variable age.

Frequency summary (number and percentage of subjects) will be provided for categorical variables including sex, race ethnicity and Fitzpatrick skin type classification.

6.5 SAFETY ANALYSIS

All subjects who received induced wounds will be included in the safety analysis. All adverse events reported during the adverse-event reporting period will be listed by subject number.

The number and percentage of subjects experiencing treatment-emergent adverse events will be presented by body system and preferred term. Treatment-emergent adverse events are those with a start date and time on or after the date and time of first use of investigational product, or the AEs start before the first use of investigational product and worsened after it. The latest version of the Medical Dictionary for Regulatory Activities (MedDRA) will be used as the adverse event classification system.

Number and percentage of subjects with serious adverse events will be summarised by MedDRA system organ class and preferred term.

Number and percentage of subjects with treatment-related adverse events will be summarized by MedDRA system organ class and preferred term. Treatment-related AEs are events evaluated by the investigator as possible, probable or very likely related to study medication. AEs with unknown relationship to treatment will be considered as treatment-related.

Number and percentage of subjects with serious adverse events will be summarized by MedDRA system organ class and preferred term.

APPENDICES

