10.4. Method of Assigning Subjects to Treatment Groups

As subjects sign a consent form, each subject will be sequentially issued a subject ID. The subject ID is an eight-digit number, beginning with the four-digit site ID “1001” and the remainder of the numerals assigned in ascending numerical order beginning with 1001, 1002, 1003, etc.

At the baseline visit, each qualified subject will be assigned a unique randomization number (e.g., 1 to 35) which determines the bandage assignment sequences. The assigned treatment will be carried out on the same wound site for Days 0 through 14. Once a randomization number has been assigned to a subject, it cannot be reassigned to another subject in that part. The assignments of the treatments and control will be based on the randomization scheme devised by the Quantitative Sciences Department at the Sponsor.

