14.4. Safety Analysis

All subjects who receive at least one dose of study treatment will be included in the safety analysis. All adverse events reported during the adverse-event reporting period will be listed by subject number and treatment. The number of subjects experiencing adverse events will be presented by body system, preferred term, and treatment. The latest version of the Medical Dictionary for Regulatory Activities (MedDRA) will be used as the adverse event classification system.

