4.3 Safety Assessments and Endpoints

Safety assessments consist of Adverse Events.

- Number and percentage of subjects with treatment-emergent adverse event
- Number and percentage of subjects with treatment-related adverse event
- Number and percentage of subjects with serious adverse event

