APPENDIX 1: SUMMARY TABLES AND FIGURES

The following tables and figures are planned for subsections in Sections 14 of the Clinical Study Report. The numbering and titles of tables and figures in this document serves as guidance; the exact numbers and titles may be modified as appropriate.

Section / Table No	Title	Population / Analysis Sets
-----------------------	-------	----------------------------

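### SAP 6.5 omits treatment from the adverse-event summary (and, less clearly, the listing) that protocol 14.4 specifies, so the tables as written do not show on which of six within-subject conditions a local event occurred

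*SAP*

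**What the plan says.** On the summary, protocol 14.4 states: "The number of subjects experiencing adverse events will be presented by body system, preferred term, and treatment". The matching sentence in SAP 6.5 reads: "The number and percentage of subjects experiencing treatment-emergent adverse events will be presented by body system and preferred term".

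On the listing, protocol 14.4 states: "All adverse events reported during the adverse-event reporting period will be listed by subject number and treatment". SAP 6.5 states: "All adverse events reported during the adverse-event reporting period will be listed by subject number".

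The SAP's summaries of treatment-related and serious events are also by system organ class and preferred term only. The safety endpoints in SAP 4.3 are counted per subject, for example "Number and percentage of subjects with treatment-emergent adverse event". SAP Appendix 1 plans three AE tables, and none of their titles has a treatment dimension. The appendix adds, however, that "The numbering and titles of tables and figures in this document serves as guidance", so the point rests on the text of SAP 6.5 and not on the titles.

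On the design, SAP 1.2 gives every subject six test sites: "Four of the test sites will be wounded and covered with various marketed adhesive bandages", one is wounded and left uncovered, and one is left intact and uncovered. Protocol 10.4 fixes treatment to site: "The assigned treatment will be carried out on the same wound site for Days 0 through 14".

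**The concern.** In a parallel-group trial, a table without treatment columns could be rebuilt from subject number and the randomization list. Here it cannot, because each subject number maps to all six conditions. Treatment is a property of the site.

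Local events are the ones for which attribution is meaningful, and the protocol anticipates them. Section 11.8.2 addresses wounds that look infected or are excessively red, painful or swollen. Section 12.2 keeps expected reactions to stripping, healing and bandage handling out of the AE data unless the investigator judges them exacerbated, so an AE of that particular kind was judged worse than expected. One of the four products in protocol Table 3 is a medicated bandage. Under SAP 6.5, a local event at that bandage, at another bandage or at an uncovered wound would enter the same count.

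**Working it through.** This is mainly a comparison of texts. The plan gives no figure to reproduce and no AE rate, so the number of events affected cannot be estimated.

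**Step 1: the two documents side by side.**

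| Output | Protocol 14.4 | SAP 6.5 |
|---|---|---|
| AE listing | subject number and treatment | subject number |
| AE summary | body system, preferred term, treatment | body system, preferred term (treatment-emergent AEs) |
| Related and serious AE summaries | not separately specified | system organ class, preferred term |

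Treatment appears in both protocol rules and in neither SAP counterpart. SAP 4.3 does not restore it, and the SAP gives no reason.

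**Step 2: what each identifier recovers.** Conditions per subject = 4 bandages + 2 controls = 6.
- Subject number only: 6 candidate conditions for a local AE, of which 4 are products.
- Subject number plus test-site number: 1 condition, because treatment stays on its site from Day 0 to Day 14.
- Subject number plus product name: 1 condition if the event is on a bandaged site. If no product applies, the two uncovered controls remain unseparated.

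**Step 3: is the site or product of an AE recorded?** Neither document says that the test site is recorded for an AE. Protocol 11.8.1 does require the strip count to be recorded per site, but there is no parallel sentence for AEs. Protocol 13.14 makes product name part of the minimum content of the serious-event form; that covers serious events only. Protocol 13.9 asks for causality to investigational product without saying which one. The AE page itself is not in the documents, so a site or product field may exist.

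**Step 4: what a pooled count can still say.** Suppose k of n subjects have a local AE in the pooled count. Every subject carries every condition, so each condition has at most k affected subjects out of n, and the upper limit for k/n is a valid though conservative bound for each product. Exact (Clopper-Pearson) two-sided 95% upper limits are the 0.975 quantile of Beta(k+1, n−k), which for k = 0 is 1 − 0.025^(1/n). Taking n from the planned 35 randomized and at least 30 completing:

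| k | n = 35 | n = 30 |
|---|---|---|
| 0 | 10.0% | 11.6% |
| 1 | 14.9% | 17.2% |
| 2 | 19.2% | – |

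With zero events, the pooled table and a by-site table give every product the same limit. With one event in 35, the pooled table allows 14.9% for every product. A by-site table would give 14.9% for the condition concerned and 10.0% for the other five. What pooling costs is knowledge of which condition was affected; a bound for each product is still available.

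**The case against.** The strongest reply is that what is established is a mismatch in planned output, not lost data. The AE page is unseen, and protocol 14.4 itself implies that some treatment attribution was meant to be collected. That stands, and a reader who infers from SAP 6.5 that attribution will be lost goes further than the documents allow.

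The listing is the softer half. Listing by subject number may describe sort order only, and SAP Appendix 2 plans Listing 16.1.7 with the randomization scheme and codes, so the site-to-treatment key will be in the report. That also stands, though the key helps only where the site or product of the event is known.

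A reader might infer that once a local AE occurs the pooled tables support no statement about any single product. They do support one, as the last step of the working shows. Nor should the Section 12.2 rule be read as making every captured local AE worse than expected: it covers expected reactions to the procedure, healing and bandages only, and those reactions are documented on the case report form in any case.

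Finally, by-treatment reporting cannot be applied literally to an event such as a headache in a subject wearing all products. This is correct and may be why the wording changed, but the SAP does not say so, and the argument does not reach events at a test site. The exploratory, unpowered nature of the study and the use of marketed bandages in healthy adults lower the weight of the point. They do not remove the inconsistency.

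**Conclusion.** The point holds as an unexplained inconsistency between protocol 14.4 and SAP 6.5. It is firm for the summary tables and weaker for the listing. Tables produced as SAP 6.5 is written would pool local AEs over four products, a wounded control and intact skin, and would not show where they occurred. For non-serious local AEs, subject number cannot recover the condition unless the test site or product was recorded, and the documents do not settle whether it was. For serious events the product name can identify a bandage but cannot separate the two uncovered controls.

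Severity is minor to moderate. The primary objective is unaffected and no safety comparison is planned; what is at stake is attribution of local harm.

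Protocol 14.4 also defines the safety population by receipt of a dose, whereas protocol 14.1 and SAP 3.3 and 6.5 use all wounded subjects. Wounding and bandaging take place at the same visit, so the sets differ only if a wounded subject leaves before any treatment starts. This is a wording matter and adds no weight.

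**What to change.** In SAP 6.5:

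1. List local AEs with test site and assigned treatment.
2. Summarize local treatment-emergent AEs, including the related ones, by assigned site treatment, using subjects with that site treatment as the denominator.
3. Report AEs not tied to a site in one overall category.
4. State that this category, and any serious-event table left pooled, depart from protocol 14.4 because the design is within-subject.

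Confirm that the AE page captures the test site, and add the field if it does not; a site not recorded during conduct may not be recoverable later. Align the safety-population wording in protocol 14.4 with protocol 14.1 and SAP 3.3 and 6.5 at the next revision.

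The cost is a few sentences in the SAP, two listing columns, treatment columns for the local AE summaries, one phrase in the protocol and possibly one data field.
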